Sample size and power analysis. The sample N of 160 was set primarily for practical and clinical reasons and not driven by estimated effect sizes or hypothesis testing. We expect to have representation (although not equal) among males and females, and across ethnic groups consistent with our current trial of TSP. We also expect to have representation across levels of smoking and drinking, and readiness to quit using both substances. We anticipate an attrition rate of 30% at 3, 6, and 12 months, yielding a final sample size of 112 (56 in each group), enabling us to compare groups on primary and secondary outcomes at each timepoint. This will also generate an effect size estimate that will be useful for powering a larger trial.

A goal of 6 participants will be recruited per week during the 6-month recruitment period, which is in line with recruitment for our feasibility trial and current RCT.¹¹¹

Procedures. Participants will be recruited through Facebook and Craigslist advertisements, using a similar strategy to that of focus group and usability-testing. All advertisements will provide a link to the study’s website, with eligibility questions. If respondents are eligible, then they will be taken to the informed consent webpage. Participants consenting to participate in the study will be asked to verify age by sending proof through email or social media, a process used successfully in [name] previous research. Verified participants will be emailed a baseline assessment. Those completing the baseline assessment will be randomized to either TSP, or TSP+ALC, stratified based on readiness to quit smoking (Ready in the next 30 days, Not Ready in 30 days) and smoking pattern (daily vs. non-daily), variables known to be related to outcomes and addressed by the intervention.¹⁶¹ A stratified random assignment program will be developed in consultation with [name], and used currently in [name] RCT of TSP. All participants will then be assigned to a secret group tailored to their condition and readiness to quit tobacco. Groups will begin when there are approximately 12 participants enrolled, as that has been deemed the optimal number based on analyses of engagement in our previous work.^{109, 162} Groups will receive one social media post daily for 90 days and weekly “The [name] In” counseling sessions managed

[figure not shown]

Figure 2. Participant flow through the study

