- **Reduction of cigarette consumption by 50% or more (y/n)** between baseline each follow-up will be calculated from the number of cigarettes smoked in the past 7 days at each time point.
- **Tobacco quit attempt (y/n)**. A *Follow-up Smoking Questionnaire* will assess the presence and number of 24 hr quit attempts since the last assessment, used to calculate presence of at least one quit attempt in the assessment time period. This questionnaire has good internal consistency and construct validity, and is routinely used in smoking treatment research.
- **Readiness to quit tobacco** will be assessed using the *Stages of Change Questionnaire*,¹²⁹ categorizing participants into five stage categories at each timepoint (precontemplation, contemplation, preparation, action, and maintenance), and predictive of quit attempts and cessation.¹⁶⁶
- **Desire to quit, abstinence self-efficacy, perceived difficulty of quitting and abstinence goal** will be assessed with the 4-item *Thoughts About Abstinence Form*,¹⁶⁷ measuring each construct on a scale from 1 ("least") to 10("most"), and categorizing goal as no goal, intermediary goal (e.g., reduced smoking), or total abstinence.

These smoking measures demonstrated significant improvement from Baseline to 12 months in the TSP feasibility trial,⁷ and have demonstrated validity for use with young adult smokers online.^{168, 169}

Secondary outcomes (alcohol):

- **Days of HED.** Past 30 day HED episodes, defined as 4+ drinks in an occasion for women and 5+ drinks for men, consistent with the NIAAA definition¹⁶ will be assessed with the *Timeline Followback* (TLFB). The TLFB has good reliability and validity for tobacco and alcohol and administered online.¹⁷⁰⁻¹⁷³ Past 30 day use is a commonly-used assessment timeframe,¹⁷⁴ and self report measures such as the TLFB can be accurate,¹⁷⁵⁻¹⁷⁷ and are the most common outcome measures for clinical trials.¹⁷⁸
- **Number of drinks per week** assessed by the *TLFB*.
- **Misuse of alcohol in the past year** will be assessed by the *Alcohol Use Disorders Identification Test-C* (AUDIT-C; 3-items; range: 0-12).¹⁷⁹⁻¹⁸¹ Used widely in the literature, cut-off scores of 3 in women and 4 in men have demonstrated good sensitivity and specificity compared to longer clinical interviews.¹⁸²

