Secondary outcomes: For secondary outcomes we will estimate and test mixed effects logistic and multinomial regression models for longitudinal ordinal response data to model secondary outcomes for tobacco use and alcohol use across time (3, 6, 12 months): 1) reduction of cigarettes by 50% or more (y/n), 2) tobacco or alcohol quit attempt (y/n; 2 models), 3) readiness to quit tobacco and alcohol (Precontemplation, Contemplation, Preparation, Action/Maintenance; 2 models); and 4) commitment to abstinence (no goal, intermediary goal, complete abstinence). In parallel, mixed effects linear regression models will model the following continuous outcomes over time: 1) past 30 day HED; 2) average number of drinks per week in the past 30 days, 3) severity of alcohol use (AUDIT-C score); 4) desire to cut down tobacco and alcohol use (1 to 10; 2 models); and 5) sum of days using either tobacco or alcohol in the past 30 days. Independent variables in all models will be treatment condition, abstinence status, and covariates identified as relevant to smoking characteristics in the literature.

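### The linear mixed models for heavy-drinking days, drinks per week and the other continuous secondary outcomes do not prespecify the baseline value of the outcome as a covariate

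*Combined protocol and SAP*

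**What the plan says.** C.9 (Secondary outcomes) states that "mixed effects linear regression models will model the following continuous outcomes over time" and lists past-30-day HED, average drinks per week, AUDIT-C score, desire to cut down each substance, and combined days of use. The responses are those at 3, 6 and 12 months. On predictors it says: "Independent variables in all models will be treatment condition, abstinence status, and covariates identified as relevant to smoking characteristics in the literature". No baseline value of any outcome is named.

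Baseline drinking could enter by two other routes, both conditional. C.9 (Preliminary efficacy) adjusts for variables found to predict attrition. The Aim 3 linear model of heavy-drinking days at 3 months adjusts for baseline differences between the arms, if there are any. Under C.8 (Procedures), randomisation is stratified on readiness to quit smoking and on daily versus non-daily smoking, not on drinking.

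C.8 (Measures) defines the HED outcome as "Past 30 day HED episodes, defined as 4+ drinks in an occasion for women and 5+ drinks for men", taken from the Timeline Followback (TLFB). On sample size, C.8 says that N was "not driven by estimated effect sizes or hypothesis testing".

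**The concern.** A participant's own earlier drinking is usually among the better predictors of later drinking. Here it is left out of the planned model, or admitted only after the data have been seen. Nothing in the stratification balances it.

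HED days most directly show what the alcohol component adds. C.8 says that the trial should yield an effect-size estimate for powering a larger trial, and C.11 ties the next grant application to better tobacco or alcohol outcomes. A needlessly wide interval for the alcohol effect therefore carries into the next trial. A rule that adjusts only when an imbalance is observed also leaves the final model open until the data are in hand.

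A lesser matter is that HED days are a count between 0 and 30, in people admitted with as little as one episode in the past month. They are probably right-skewed, although the documents do not show this.

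**Working it through.** **Inputs from the documents.** N = 160, 30% attrition and 56 per group (C.8, Sample size); responses at 3, 6 and 12 months (C.9).

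**Assumptions, none from the documents.** Two-sided alpha 0.05; a true difference of d = 0.4 single-visit SDs; a correlation ρ of 0.3, 0.5 or 0.7 between baseline and each follow-up, and between follow-ups; 56 per arm with complete data.

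**Step 1: the plan's own figure.** 160 × (1 − 0.30) = 112, and 112 / 2 = 56 per arm. This reproduces. The plan gives no power or detectable effect to check.

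**Step 2: one visit.** Without baseline, the standard error in SD units is √(2/56) = 0.189, and power is Φ(0.4/0.189 − 1.96) = Φ(0.157) = 56%. Adjusting for baseline multiplies the standard error by √(1 − ρ²). The equivalent unadjusted sample is 56/(1 − ρ²), and the 95% half-width is 1.96 × 0.189 × √(1 − ρ²).

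| ρ | Power | Gain (points) | Detectable d at 80% power | Half-width (SD) | Equivalent n per arm |
|---|---|---|---|---|---|
| no baseline | 56% | – | 0.53 | 0.37 | 56 |
| 0.3 | 60% | 4 | 0.50 | 0.35 | 62 |
| 0.5 | 69% | 12 | 0.46 | 0.32 | 75 |
| 0.7 | 84% | 28 | 0.38 | 0.26 | 110 |

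**Step 3: mean of three visits.** This approximates a mixed model with one treatment effect across visits. The variance factor is (1 + 2ρ)/3 without baseline and (1 + 2ρ)/3 − ρ² with it.

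| ρ | Factor without | Factor with | Power without | Power with | Gain (points) |
|---|---|---|---|---|---|
| 0.3 | 0.533 | 0.443 | 83% | 89% | 6 |
| 0.5 | 0.667 | 0.417 | 74% | 91% | 17 |
| 0.7 | 0.800 | 0.310 | 66% | 97% | 31 |

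**Step 4: chance imbalance.** With 56 per arm, the difference in mean baseline drinking has standard error 0.189 SD. It exceeds 0.2 SD in either direction with probability 2 × [1 − Φ(0.2/0.189)], about 29%.

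**Step 5: does the error distribution matter?** HED days at one visit were simulated as overdispersed counts capped at 30, with baseline at least 1, 56 per arm, a mean parameter of 4 to 5 days and a rate ratio of 0.65 (800 runs per scenario). Skewness was about 1.7 to 2.2. The linear model used raw baseline; the negative binomial (NB) model used log baseline and no small-sample correction. The figures are power.

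| Observed correlation | Linear | Linear + baseline | NB | NB + baseline |
|---|---|---|---|---|
| 0.23 | 54% | 55% | 59% | 59% |
| 0.40 | 40% | 45% | 46% | 53% |
| 0.53 | 50% | 62% | 57% | 68% |
| 0.60 | 40% | 55% | 48% | 61% |

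Type I error was 3 to 5% for the linear model, with or without baseline, and about 5 to 8% for NB. Monte Carlo error is about 1.7 points on power and 0.8 on type I error. Baseline alone adds about 1, 5, 12 and 15 points to the linear model as correlation rises. Changing only the error distribution adds about 5 to 8, part of which reflects the liberal NB test.

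**The case against.** The strongest reply is that this is a pilot. These are secondary outcomes, no power is claimed for them, and N was not set by hypothesis testing. That stands. It makes the cost one of precision rather than a missed power target, but precision is what an effect-size estimate for the next trial needs.

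Second, the plan does contain adjustment routes. They exist, but both depend on what the data show, and neither guarantees that baseline drinking enters the secondary models.

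Third, the gain rests on an undocumented correlation. That also stands: near 0.3 the gain is small.

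Fourth, the text does not say outright that the TLFB is given at baseline. C.8 plans a baseline assessment, and C.9 (Feasibility) will describe the drinking characteristics of those enrolled, so a usable baseline measure is likely but should be confirmed.

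A reader might go further and infer that normal-error models for skewed counts make the drinking analyses invalid, or cost much power in themselves. The documents give no distribution for drinking, and in the simulations the linear model kept its type I error at 56 per arm. From a correlation of about 0.5 the baseline covariate brings the larger gain; below that neither change brings much, and the NB advantage is partly inflated. Nor does it follow that an NB model should be the main analysis. It can predict more than 30 days, so it does not respect the upper bound either. Average drinks per week is not an integer count and was not simulated.

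**Conclusion.** The point holds as one about precision. C.9 does not prespecify the baseline value of the outcome in the linear mixed models for the continuous secondary outcomes, and nothing elsewhere ensures it. The planned linear test is valid.

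Under the stated assumptions, the loss ranges from minor at a correlation of 0.3 (4 to 6 power points) to large at 0.7 (28 to 31). At 0.5, adjustment is worth about 19 extra participants per arm at a single visit (75 against 56). A flat statement that the plan loses substantial power would go beyond the documents, which give no drinking SD, skewness or baseline correlation. The choice of error distribution is secondary and merits a sensitivity analysis, not a new main model.

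**What to change.** In C.9 (Secondary outcomes), state that each continuous outcome's model includes the baseline value of that outcome, whether or not the arms differ or the value predicts attrition. For HED days and drinks per week, use the past-30-day TLFB value at baseline, and state in C.8 (Measures) that the TLFB is given then.

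Add two sensitivity analyses, each with the baseline covariate and small-sample-corrected errors: a log-link count model for HED days, and a log-link model with robust errors for average drinks per week. Because these give ratios, also report the model-based mean difference.

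If the TLFB is already taken at baseline, the cost is wording and a little extra analysis, with no new data. If it is not, it must be added to the baseline survey.

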While preliminary work is not necessary for a Planning Grant application (R34), our team has pilot data and expertise that is directly relevant to this application.

Development, feasibility and efficacy of the Tobacco Status Project (TSP). During her postdoctoral fellowship, [name] led a mixed-methods study to determine how young adult smokers would like to use Facebook to help change smoking behavior. About a third (31%) of survey respondents reported they would want to quit smoking using Facebook, and interest was greater among those more motivated to quit, who had made a quit attempt in the past year, and had previously used the Internet for assistance with a quit attempt (all $p<0.01$). In qualitative interviews, social support and convenience were identified as strengths of a Facebook intervention, while privacy was the main concern.⁴

[name] is currently funded with a five-year K23 career development award from NIDA to develop and test the feasibility and efficacy of Tobacco Status Project, combining Facebook contacts tailored to participants' readiness to quit smoking with a 12-week cessation program consisting of 7 state-of-the-art group cognitive-behavioral sessions occurring over Facebook text chat. A feasibility trial enrolled 79 young adults who formed 7 Facebook groups. Follow-up rates were 84% and 72% at 6 and 12 months, respectively, and reported 7-day abstinence was 21% at 6 months (9% biochemically-verified) and 18% at 12 months (9% verified).^{6,7} From baseline to 12-months, there was a significant increase in the proportion prepared to quit (13% to 46%, $p<.001$), 35% reduced their cigarette consumption by 50% or greater, and 67% reported a 24-hr quit attempt. Engagement in the intervention was high, with 92% participation in the full 3 month intervention and 61% commented on at least one post, with more commenting among those randomized to receive a personal monetary incentive.¹⁰⁹ Participants reported reading most of the Facebook posts (mean usability rating=3.3/4) and interactions from counseling sessions (3/4), thinking about what they read (3/4) and would recommend the program to others (3.3/4). Given low participation in CBT sessions (7 of 79 participated) but extremely high engagement (6/7 sessions attended on average) we incorporated the sessions directly into the Facebook groups for a larger efficacy trial currently underway.

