Participants. Participants will be 20 young adult men and women who: 1) read English; 2) are between 18 and 25 years of age; 3) indicate they use Facebook "most" (≥ 4) days per week; 4) have smoked ≥ 100 cigarettes in their lives and currently smoke at least 1 cigarette per day on 4 or more days of the week; 5) have had at least one heavy drinking episode (5+ for men, 4+ for women) in the past month. Smoking criteria are based on those used in the National Health Interview Survey¹² and are liberal based on smoking patterns most common in young adults and to include ethnic/racial minority populations, who tend to smoke fewer cigarettes per day than Caucasians.¹²

Procedure. Participants will be recruited through Facebook and Craigslist advertisements, using a design and targeting strategy used successfully by the PI with young adult smokers.¹¹⁰⁻¹¹² Eligibility and consent will be evaluated online through a Qualtrics survey housed on UCSF secure servers. Once consented, participants will be invited to join a focus group, through a private event conducted on Facebook.

[figure not shown]

Figure 1: Study design

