through the study's private group pages. If participants wish to have private study interactions with study staff they can do so at any time. Three-month follow-up assessments will be emailed to participants upon completion of treatment.

Informed consent, baseline and 3, 6, and 12 month assessments will be delivered using the online survey program Qualtrics, which is HIPAA-compliant, has been used often in medical research, and is being used successfully by [name] for her current Facebook intervention study. Verification of non-smoking status will be conducted for all participants reporting no smoking in the past 7 days at the post-test assessment using mailed saliva cotinine test kits and verified online as described in the **Measures** section. Participants will receive their choice of Amazon or Best Buy gift cards in the amount of \$20 for each 20-30 minute online survey, and a bonus \$20 for completing all assessments, for a total of \$100 possible compensation for participation. Amazon and Best Buy were chosen as retail outlets given their overwhelming popularity among a large choice of retailers given in [name] previous studies with young adult smokers.^{4, 111} Assessments will not be considered complete until staff receives verification of abstinence.

Measures.

Primary outcome (tobacco):

- **Biochemically-verified 7-day point prevalence abstinence from all tobacco products** will be assessed at 3, 6, and 12 months. Participants reporting no smoking in the past 7 days will be coded as abstinent from cigarettes. Those reporting 7-day abstinence will be mailed a saliva cotinine test kit, and record two pictures: one giving a saliva sample, and another of the test result. Participants with a salivary cotinine level <11 ng/ml, indicating nonsmoking,¹⁶³ will be considered confirmed nonsmokers. Biochemical verification is recommended in randomized trials with sample sizes under 500,¹⁶⁴ saliva cotinine test kits have been successfully mailed to participants in previous studies,¹⁶⁵ and [name] is using this method successfully in her K23 Facebook smoking cessation RCT with young adults (to date, 50% reporting 7-day abstinence have successfully completed biochemical verification). If participants indicate use of an electronic nicotine delivery-system to aid in smoking cessation, saliva cotinine and reported ENDS use will be recorded and reported separately from biochemically verified abstinence.

Secondary outcomes (tobacco):

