- **Alcohol quit attempt (y/n)**. A *Follow-up Drinking Questionnaire* will assess the presence and number of 24 hr quit attempts since the last assessment, used to calculate presence of at least one quit attempt in the assessment time period.

- **Readiness to change alcohol use** will be assessed with a single-item **Readiness Ruler**, developed and validated for use with young adult heavy drinkers participating in brief intervention.^{183, 184} and the alcohol item from the **Staging Health Risk Assessment (S-HRA)**^{185, 186} to compare stage of change across tobacco and alcohol use.
- **Desire to quit HED, abstinence self-efficacy, perceived difficulty of quitting and abstinence goal** will be assessed with an adapted *Thoughts About Abstinence Form* for HED.
- **Thoughts about alcohol** will be assessed the *Thoughts About Abstinence* form, adapted for alcohol.

Secondary outcome (combined days using tobacco or alcohol):

- *TLFB* data will be used to calculate the sum of days using any tobacco or binge drinking in the past month.

Additional measures.

- **Demographics.** Age, gender, ethnicity, parental and personal education, work/school status, military involvement, parental status, and other personal characteristics will be assessed at baseline with a *Demographic Questionnaire* used in our prior research with young adults.¹⁶⁹
- **Smoking History.** The *Smoking History Questionnaire*¹⁵⁸ at baseline will assess age of initiation and years of smoking; prior quit attempts and cessation strategies; other nicotine (e.g., electronic nicotine delivery systems) and tobacco use (e.g., cigars); nicotine dependence using the 6-item *Fagerström Test of Cigarette Dependence (FTCD)*,^{187, 188} and social smoking with 3-items used with young adults.^{189, 190}
- **Alcohol Use history.** We will assess age of first drink and first heavy drinking episode, prior attempts to change HED, and change/cessation strategies.
- **Combined alcohol and tobacco use.** Two items assessing subjective effects of smoking while drinking (estimated overlap and pleasure), previously used with college students,³⁴ will be given at baseline.
- **Drug Use Severity.** The *Drug Abuse Screening Test-10* (DAST; 10 items),¹⁹¹ will assess misuse of drugs in the past year. Used widely in the literature, a cut-off score of 2 has demonstrated good sensitivity and specificity compared to longer clinical interviews.¹⁹²

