Feasibility analyses will examine four areas: **(1) Recruitment Efforts:** We will evaluate (a) length of time to recruit N=160 participants to enroll in the pilot trial, and (b) demographic, smoking, and drinking characteristics of those eligible and who enroll; **(2) Usability:** We will calculate mean responses to Likert scale items of the usability measure and any sections with lower than median values will indicate changes should be made before future investigations take place. **(3) Implementation of biochemical verification of tobacco abstinence:** We will determine the proportion of participants in each condition reporting 7-day point prevalence abstinence at 3-month follow-up that completes a saliva cotinine test and the rate of discordance between saliva cotinine results and self-report. **(4) Attrition:** We will track the number and proportion of participants that completes each follow-up assessments and compare these numbers to previous Internet cessation trials (attrition as high as 75%^{52, 53, 199-201}).

Analyses for Specific Aim 2: Preliminary efficacy.

Descriptive statistics will summarize sample characteristics and the extent of intervention delivery in each group. We will examine treatment condition and baseline descriptive characteristics as predictors of

attrition at trial end (month 3) and propose to control for predictors of attrition as covariates in model testing. Missing data will be minimized through online assessment. When subjects do not complete online assessments, they will be re-contacted through Facebook or email to obtain missing information. For each test related to smoking, two sets of outcome analyses will be conducted - one with all participants who are maintained in the study, and another based only on biochemically verified smoking abstinence rates to allow for direct comparison of findings with the research literature.

Primary outcome: To test for the effects of treatment condition on smoking abstinence at 3- through 12-months, we will estimate and test a mixed-effects logistic regression model. Abstinence status will be examined as 7-day point prevalence. The independent variables are TSP versus TSP+ALC plus variables that are related to abstinence such as cigarettes per day, differ by condition at baseline or predict attrition. We will use multiple imputation procedures to impute missing data.

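### Secondary models adjust for smoking abstinence after randomisation (the primary endpoint), so they do not in general estimate the total effect of TSP+ALC versus TSP

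*Combined protocol and SAP*

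**What the plan says.** C.9, Secondary outcomes, fixes the covariates for every secondary model at 3, 6 and 12 months: "Independent variables in all models will be treatment condition, abstinence status, and covariates identified as relevant to smoking characteristics in the literature".

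The paragraph just before it, on the primary outcome, defines the term: "Abstinence status will be examined as 7-day point prevalence". C.8, Measures, gives the coding: "Participants reporting no smoking in the past 7 days will be coded as abstinent from cigarettes". Assessment is at 3, 6 and 12 months, and the cotinine-verified form is the primary endpoint.

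On timing, C.8 Procedures says "Those completing the baseline assessment will be randomized to either TSP, or TSP+ALC". The entry criteria in C.4, which C.8 carries over to the trial, require that participants "currently smoke at least 1 cigarette per day on 4 or more days of the week".

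Two secondary outcomes are built partly from smoking itself. The 50% reduction outcome "will be calculated from the number of cigarettes smoked in the past 7 days at each time point". For the combined outcome, Timeline Followback data are used to "calculate the sum of days using any tobacco or binge drinking in the past month".

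**The concern.** Abstinence status cannot be a baseline covariate, because nobody is abstinent at entry. It is measured after randomisation, and the intervention is meant to change it. Conditioning on it removes whatever part of the treatment effect works through quitting. It can also add bias if an unmeasured factor, such as motivation, drives both quitting and the outcome. That is acceptable in a declared mediation analysis. C.9 declares none and plans no secondary model without the covariate.

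C.3 says Phase II compares the arms on smoking and drinking outcomes. C.8 (Sample size) says the arms will be compared on secondary outcomes and that an effect size will be generated for a larger trial. C.13 plans a trial powered on both tobacco and alcohol outcomes. These uses call for the total effect. If TSP+ALC helps people quit, the models as written would leave that benefit out of the outcomes that contain smoking.

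**Working it through.** **Plan's own figure.** 160 × (1 − 0.30) = 112 retained, 56 per arm, as C.8 states. The plan gives no power or effect size to reproduce.

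**Inputs.** Feasibility trial, in the preliminary-work section: "35% reduced their cigarette consumption by 50% or greater"; at 12 months 18% reported abstinence and 9% were verified. For illustration only, a 3.2-point difference in abstinence (13.5% vs 10.3%) from the adult quitline trial described in Section A. The 35% is taken to include abstainers, as the C.8 definition implies; the alternative is shown.

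**1. Reduction of 50% or more: what is lost without assuming any treatment effect.** Someone abstinent at a visit smoked no cigarettes in the same 7 days, so the outcome is yes by definition. This holds for verified abstainers too, because they are a subset of those reporting no smoking. With same-visit abstinence in a logistic model, its coefficient diverges, abstinent visits drop out of the likelihood, and the treatment odds ratio (OR) comes only from non-abstinent visits.
- Abstainers among reducers: 0.18/0.35 = 51%; verified 0.09/0.35 = 26%.
- All completers: 112 × 0.35 = 39 reducers in 112.
- Non-abstinent, 18% abstinent: 112 × 0.17 = 19 reducers in 112 × 0.82 = 92.
- Non-abstinent, 9% abstinent: 112 × 0.26 = 29 reducers in 112 × 0.91 = 102.
- One-visit SE of the log OR, 56 per arm: √(2/(56 × 0.35 × 0.65)) = 0.40. Among non-abstainers only it is 0.51 (18%) or 0.44 (9%).

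**2. Same outcome with a 3.2-point gain (18.0% to 21.2% abstinent), one visit.**
- Added quitters would not otherwise have reduced: total OR (0.382/0.618)/(0.35/0.65) = 1.15. Among non-abstainers, 0.17/0.82 = 20.7% vs 0.17/0.788 = 21.6%, OR 1.05.
- Added quitters drawn evenly from non-abstainers: 0.212 + 0.2073 × 0.788 = 37.5% reduced, total OR 1.12; conditional OR 1.00.
- If the 35% excludes abstainers (53% reduced in all): 1.14 becomes 1.07, or 1.08 becomes 1.00.
- Shift on the log scale: ln 1.148 − ln 1.052 = 0.087, and ln 1.116 = 0.110. Divided by 0.40, these are 0.22 and 0.28 of an SE.

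**3. Three visits with a random intercept, as planned.** This was a simulation of 2,000,000 subjects with an assumed within-person latent correlation of 0.3 to 0.7. The total OR of 1.19 to 1.31 becomes 1.06 to 1.09; with the even draw, 1.14 to 1.24 becomes 1.00 to 1.01. These are subject-specific ORs. The log shifts are 0.11 to 0.20. The SE at 112 participants is about 0.33, 0.43 and 0.62 for correlations 0.3, 0.5 and 0.7, so the shifts are about 0.3 to 0.4 of an SE.

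**4. Linear models.** Adjusted effect = total effect − (abstinence coefficient × arm difference in abstinence). This is exact for least squares with these two terms and approximate with further covariates and random effects. If treatment does not change abstinence, the two effects agree.
- Combined days, assuming 4, 7 or 30 tobacco days avoided per quitter (entry minimum in one week, a daily smoker's week, a full month): 0.032 × 4 = 0.13, 0.032 × 7 = 0.22, 0.032 × 30 = 0.96 days per participant removed.
- Heavy-drinking days: 0.03 days (one fewer day per quitter, no shared cause) to 0.19 days (four fewer, with shared motivation, by simulation). These values rest wholly on assumptions. With an assumed SD of 4, the SE is √(2 × 16/56) = 0.76 days, so the shift is 0.04 to 0.25 of an SE.

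**The case against.** The strongest reply is that this is peripheral. It is a pilot whose sample size was not set by hypothesis testing. The Aim 3 text in C.9 names abstinence and heavy-drinking days as the main tobacco and alcohol outcomes; the first is unaffected and the second probably moves little. The outcomes most affected are not named as endpoints for the next trial, and the shift lies well inside sampling error. This stands as a limit on severity. It does not make the covariate right: C.8 promises comparisons on the secondary outcomes, and a larger sample would not remove the shift.

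Further points narrow the claim:
- C.9 does not say whether abstinence is concurrent or lagged. The perfect prediction in step 1 needs concurrent status, which is the more natural reading. Under either reading the variable is post-randomisation.
- The counts of 19 in 92 and 29 in 102 combine two feasibility percentages whose denominators are not given. They describe one visit and completers, whereas the plan pools three visits and mentions multiple imputation under the primary outcome.
- Tobacco quit attempts do not overlap with abstinence by definition. With 67% attempting and 18% abstinent, abstainers are at most 0.18/0.67 = 27% of attempters. Attempts are also counted since the last assessment, so a sustained abstainer may report none. Tobacco readiness should overlap more, through the Action/Maintenance category, but no figure is available.
- If combined days count a day once when either behaviour occurs, a quitter's drinking days still count, and 0.96 is an extreme bound.

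No other part of the plan repairs the problem. The two sets of smoking analyses in C.9 contrast all retained participants with verified abstinence, and the Aim 3 regressions relate engagement to 3-month outcomes. Neither gives a secondary treatment comparison free of this covariate.

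**Conclusion.** The concern holds. As written, all secondary models condition on the primary endpoint measured after randomisation, so their treatment coefficients do not in general estimate the total effect. For 50% reduction, with concurrent abstinence, the definitions alone establish the problem, and about half of reducers (a quarter if verified) stop informing the treatment comparison at the feasibility rates. The attenuation (1.15 to 1.05, or 1.12 to 1.00, at one visit) depends on the assumed 3.2-point gain and on who the added quitters are. For combined days the amount removed is 0.13 to 0.96 days under the stated range. For drinking outcomes the shift is probably small, and its size and direction depend on assumptions. It should be corrected before analysis, but it does not threaten the main result of the pilot.

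**What to change.** In C.9, Secondary outcomes, delete abstinence status from the independent variables of all treatment-effect models and keep only covariates measured before randomisation. If the role of quitting is of interest, add one sentence placing it in a separate exploratory mediation analysis, labelled as such and not used as the treatment comparison. The cost is one phrase deleted and at most one sentence added, with no new data and no change to the sample size.
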